5.3 Informed Consent Procedures

A waiver of informed consent and HIPAA authorization will be used for recruitment and screening purposes. A waiver of documentation of consent and HIPAA authorization will be used to retain the preliminary eligibility screening responses (*see Screening Script*). Informed consent will be obtained prior to enrollment in the study.

The Research Coordinator, the PI, and/or other designated staff, as indicated on the study staff form, will conduct the informed consent process. All study personnel will complete the necessary human subjects protections training per VA policy.

5.4 Inclusion/Exclusion Criteria

Inclusion Criteria:

- 1) Age 18-79 years
- 2) Unilateral transtibial amputation
- 3) Been fit with a prosthesis and used it for at least 6 months
- 4) Wear the prosthesis for 4 or more hours on average per day
- 5) Ambulate without upper extremity aids
- 6) Able to walk for 30 minutes on a treadmill

Exclusion criteria:

- 1) Improper fit and suspension with current prosthesis and one cannot be achieved with clinical resources (determined at initial visit)
- 2) Current skin irritation or injury on residual limb
- 3) Osteoarthritis, injury, or pain that interferes with walking ability
- 4) Currently incarcerated
- 5) Pregnant (determined via self-report)

- 6) Inadequate cognitive function or language proficiency to consent to participate
- 7) High (>20%) coronary heart disease risk at 10 years as determined by their Framingham Risk Score

5.5 Study Visits, Data Collection

Visits and length of participation

Consent and data collection procedures will be done at the VA Puget Sound in Seattle. Participants will be asked to do 4-7 visits that may span up to 2 months. If we find that data are missing or corrupt participants may be asked to do another study visit. All procedures are for research purposes and provide no clinical treatment. Participants will be provided rest breaks throughout the procedures and may request one at any time. We may call and/or email participants to remind them about upcoming study visits. Participants will be asked to not consume caffeine, tobacco, and alcohol for two hours prior to each visit and not apply anything to their skin for 12 hours before the visit.

Data Collection Protocol

Baseline Visit

Demographics

We will ask participants to provide us with the following demographic information:

- age
- years since amputation
- side of amputation
- cause of amputation
- body weight
- height
- as prescribed prosthesis (socket type, liner, suspension system, foot type, category and size)

Skin Health and Socket Comfort

To collect baseline data, participants will be asked to take off their prosthesis while seated in a climate-controlled room set to 68 °F/20 °C, 50% relative humidity. Their residual limb will be dried with a towel (if needed). After sitting for 15 minutes, we will use specialized equipment to measure participants' skin health (skin hydration level and transepidermal water loss) by touching a few places on their legs with the instrument's hand-held measurement tools/probes. The average results from these measurements will be the participants' baseline skin health for their as-prescribed prosthesis. If subjects have thick leg hair, we may need to shave a small patch to allow the instrument to get a good reading. Participants will also be asked rate their how comfortable their socket is on a 0-10 scale.

Self-Selected Walking Speed

While using their own prosthesis, participants will be asked to walk back and forth down an unobstructed 65ft/20-m hallway several times. These trials will allow us to determine participants' self-selected walking speed.

Prosthetic Fitting

Our research prosthetist may begin the fitting process for the two study prostheses during the baseline visit, but this process may take place over 2-3 visits. Once both study prostheses fit well, participants will be randomly assigned to wear either the perforated prosthetic liner system or the novel prosthesis during their usual daily activities for two weeks. During the daily use periods, participants will be instructed to check their limb for redness and/or irritation twice a day and if they notice any issues they should contact us immediately for instructions. We will assist with arranging any necessary follow-up care as needed.

Step Count

During the daily use periods, an electronic step counter, taped to the prosthetic pylon/ankle, will collect step-count data. The step data will be collected from the counter when participants return for the next study visit.

Heart Disease Risk Screening Test

During the baseline or prosthetic fitting study visits, prior to the treadmill walk in the 95°F temperature condition, we will screen participants for cardiac problems. We will use the Framingham Risk Score calculator (<https://www.mdcalc.com/framingham-coronary-heart-disease-risk-score>), an age and sex-specific algorithm that calculates the risk for developing cardiovascular disease at 10 years. Participants who have a high (>20%) coronary heart disease risk at 10 years will be withdrawn from the study. The screening test requires the following information: age, sex, smoker, currently on any medication to treat high blood pressure, systolic blood pressure, total cholesterol, and high-density lipoproteins (HDL) cholesterol. The first four items will be obtained by self-report. Systolic blood pressure will be measured with an existing portable digital blood pressure monitor. Total cholesterol and HDL cholesterol results, from within the last 2 years, may be obtained from VA or UW medical records, another medical facility via a release of records request, participant self-report, or by blood draw at the VAPSHCS clinic. If we determine that a participant's risk of heart problems is too high for this study we will advise them to follow-up with their regular medical care provider, and they will not be able to participate further in the study. If a participant is unable to continue in the study, they will be compensated for their effort.

Visit: Study Prosthesis 1

After two weeks of using the first study prosthesis, participants will return to the VA for a data collection visit. Participants will be instructed to drink approximately 8 to 15 ounces of water two

hours before their study visit and to bring a pair of shorts and a t-shirt to wear, but we will provide this clothing if they prefer. We will repeat the procedures described above in the Baseline Visit to measure skin health and Socket Comfort Score.

While the prosthesis is off, we will make sure the socket and other key components are dry and we will weigh them. Participants will be provided with fresh/dry socks to wear during the procedures. Participants will be asked to change into the shirt and shorts and put the prosthesis back on. A private area to change will be provided. Participants will be asked to wear a wristwatch-style heart rate monitor during the study visit. We will also place a small absorbent pad on the calf of the intact leg to collect sweat. The pad will be attached to the skin using a sticky waterproof covering to prevent evaporation. We will also draw a mark on the skin of the residual limb at the top edge of the socket liner so we can measure how much the liner slips.

When ready, participants will enter the climate-controlled space set at 35° C (95 °F) and 50% relative humidity. Participants will sit for a 30-minute acclimation period and will then be asked to walk on a treadmill at their pre-determined self-selected walking speed for up to 30 minutes or until they feel like the prosthesis may slip off. The duration of activity will be timed, but we anticipate all participants will be able to walk for 30 minutes. Participants will be allowed to drink water as desired during the trial, and we will record the amount of fluid they drink. Handrails and a chair will be present in case participants feel unsteady or wish to take a break.

For safety purposes, we will track participants' heart rate (via the wristwatch monitor) throughout the test. For participants who do not take a beta-blocker medication (self-report), we will stop the test if their heart rate exceeds 75% of their age-adjusted maximum heart rate (220 minus age in years) for 3 consecutive minutes. For participants who do take a beta-blocker medication, we will stop the test if their heart rate exceeds 110 beats per minute for 3 consecutive minutes.

[figure not shown]
When the treadmill walk is done, we will have participants sit and rest in a space with a comfortable climate (68 °F/20 °C, 50% relative humidity) for up to 30 minutes, and we will measure the prosthetic liner slippage. Participants will be asked to take off the prosthesis and then we will re-weigh the key components. We will also dry off participants' residual limb with an absorbent towel to collect the sweat remaining on the skin and remove the absorbent pad from the other leg. We will weigh the towels, prosthetic components, socks, and absorbent pad to see how much moisture the participants lost on their lower limbs by sweating.

We will put the step counter on participants' as-prescribed prosthesis. Participants will then be fit with their As-Prescribed prosthesis and asked to use it during their usual daily activities for the next two weeks.

Visits: As-Prescribed Prosthesis & Study Prosthesis 2

After the 2-week use period, participants will come back to the VA and, using their As-Prescribed prosthesis, they will do the same procedures they did with Study Prosthesis 1. At the end of the

visit, participants will be fit with the other study prosthesis then repeat the 2-week use period and the data collection visit.

During study sessions, visitors and observers will not be allowed in the lab unless the participant agrees to their presence; the participant can change her/his mind at any time.

Photos and Video

We may take video and photos of participants during portions of this study for documentation and use in research publications. To protect the identity and privacy of our participants, all videos and photos will be edited later to de-identify the images (e.g., blurring of faces, tattoos, and other distinguishing marks). No sound will be recorded to prevent voice identification.

Repository

Participants will be asked if they are interested in allowing their study data to be added to our de-identified data repository so that it may be used for additional research in the future. Participants who are interested will be asked to sign a separate consent form for the repository (MIRB# 00493). Once the consent form is signed, and after a PRAF to MIRB# 00493 to accept the data has been approved, a copy of the data will be added to the repository on an ongoing basis throughout the course of the study.

Payment to Participants

Participants will receive \$600 for participating in the study. Participants will be paid after their participation in the study is finished. Payments will be made by check. Checks will be mailed out 2-8 weeks after participants' last visit or they can make arrangements to pick up their payment at the VA Puget Sound within the same timeframe. If participants are screened out or withdraw prior to finishing all study procedures, we will compensate them on a prorated basis based on the number of visits/how many of the study procedures they completed.

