Compare three different, lower limb prosthetic systems and identify which is most effective at maintaining a secure adherence when worn in conditions that result in profuse perspiration.

Our hypotheses related to the first specific aim include:

H_{1.1} The amount of slippage (loss of adherence) will be different between the three prosthetic systems. Measurements of the prosthetic liner position relative to the residual limb will be recorded (before and after) and the differences will be compared.

H_{1.2} The amount of perspiration expelled will be different between the Uniprox and DAE-RED. Tare weighing (before and after) of all prosthesis components will be performed and the remainder, after subtracting the amount accumulated inside, will be compared.

Specific Aim 2:

Compare how three prosthetic systems effect residual limb skin health and comfort when participants pursue their usual activities in the home, work, and community environments.

Our hypotheses related to the second specific aim include:

H_{2.1} Residual limb skin hydration will be different between the three prosthetic systems. After doffing the prosthesis, we will use a specialized instrument (Corneometer) to measure skin hydration, a measure of skin dryness. The results between prostheses will be compared.

H_{2.2} Residual limb transepidermal water loss will be different between the three prosthetic systems. After doffing the prosthesis, we will use a specialized instrument (Tewameter) to measure transepidermal water loss, a measure of skin barrier disruption. The results between prostheses will be compared.

H_{2.3} The Socket Comfort Score will be different between the three prosthetic systems. Individuals can have strong opinions about their prosthesis. To assess comfort, we will ask subjects to rate their socket comfort on a 11-point scale, and the results between prostheses will be compared.

4. Resources and Personnel

Data collection procedures for this study will be conducted at the VA Puget Sound in Seattle, WA. See Study Staff Sheet attachment for listing of personnel, ability to obtain consent, and access to PHI.

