5.6 Risks and Risk Management

Please note, the increase in physical risks associated with participation in this study only represent a small increase from those encountered in daily life of the participant population.

It is possible that participants may experience an injury (e.g., arising from a trip or a fall while walking on a treadmill or while wearing a study provided prosthesis during the at-home acclimation periods) and/or discomfort (e.g., mild to moderate muscle soreness, excessive skin dryness, blisters, or other soft tissue irritation while in the lab or during the at-home acclimation period), because of walking with the study-provided prostheses. It is possible that a component failure or malfunction of the prostheses could cause a soft tissue injury (e.g., soreness, bruising, scrape) or other minor mechanical injury (e.g., knee or ankle joint soreness). Care will be taken to properly fit the prostheses. Only trained study staff will place and remove the guaze for trapping moisture to mimimize risk of injury. Participants will only be asked to walk on the treadmill at a speed they are comfortable with. To minimize the risk of study prostheses failure, these devices will be thoroughly tested on a benchtop and a certified prosthetist will also evaluate the quality of the prostheses prior to them being worn by participants. Additionally, most of the prosthetic componentry are commonly used, commercially-available devices. Participants will be instructed to exhibit caution while acclimating to walking with a new or modified prosthesis, and they will be asked to check their skin for redness and/or skin irritation twice a day during the daily use periods. If skin issues arise participants will be instructed to contact study staff. These are the same instructions provided when a patient receives a new or different prosthesis as part of a clinical prescription. Since participants will have a chance to wear each of the study prostheses prior to wearing them home, we do not expect any problems to arise during the two-week at-home portion of the study. Participants will be asked to contact us immediately in the event of any study-related pain or injuries to schedule an examination.

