The PI will ensure the study procedures are being properly followed by keeping the research staff well informed of the current study procedures through regular/ongoing contact. Although an injurious fall or a prosthetic component failure related to this protocol is unlikely, we will tabulate a list of any such reports that occur during the study and compare it with corresponding data available in the literature. This will allow us to analyze how much of an increased risk was due to the administered protocol. After each report of an AE, SAE or an unanticipated problem, we will evaluate study procedures for previously-assessed risks, and will determine whether any changes to the protocol are necessary to minimize risks. The use of any procedures or equipment determined to be problematic will be suspended until these changes have been fully implemented and approved by the IRB.

Privacy and Confidentiality

See section 7.0 below for Information Security, Privacy, and Confidentiality related procedures.

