5.7 Data Analysis

Data collected from the laboratory-based experiments will be used to test three hypotheses. The distance that the proximal border of the liner moved from its pre- to post-treadmill walk in the environmental chamber position (marked on the skin) will be compared and enable us to test hypothesis: (H_{1.1}) *The amount of slippage (loss of adherence) will be different between the three prosthetic systems.* The tare weight (wet – dry conditions) of perspiration expelled from Uniprox and DAE-RED prostheses will be compared and enable us to test hypothesis: (H_{1.2}) *The amount of perspiration expelled will be different between the Uniprox and DAE-RED.*

Data collected from the field-based experiments will be used to test three hypotheses. The mean result from the three measures of skin hydration from the posterior compartment of the residual limb will be compared and enable us to test hypothesis (H_{2.1}) *Residual limb skin hydration will be different between the three prosthetic systems.* The mean result from the three measures of transepidermal water loss from the posterior compartment of the residual limb will be compared and enable us to test hypothesis (H_{2.2}) *Residual limb transepidermal water loss will be different between the three prosthetic systems.* The Socket Comfort Score will be used to access the comfort of the three prosthetic systems and enable us to test hypothesis (H_{2.3}) *The Socket Comfort Score will be different between the three prosthetic systems.*

The statistical analysis to test these hypotheses will require six linear mixed effects regression analyses. These analyses will test for differences by prosthetic system (as-prescribed, Uniprox, DAE-RED) with random effects for subject and subject by prosthetic system interaction. The experiment-wise significance will be set a priori at an alpha level of $p<0.05$ and a Bonferroni adjustment will be applied for multiple comparisons. All analyses will be performed using existing software (R Foundation for Statistical Computing with lme4 and multcomp packages, Vienna, Austria). Exact p-values will be reported for each test.

Statistical Power Analysis

We conducted several power analyses to explore the statistical strength of our study design and estimate the number of subjects necessary to obtain meaningful results.

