5.8 Withdrawal of Subjects

This is not a treatment study; withdrawing or being terminated from this study will not have an impact on participant safety. A study clinician or the PI may withdraw a participant without their consent if he or she feels that it is not in a participant's best interest to continue in the study or the person is unable to complete the study procedures. All data previously collected from participants who withdraw or are withdrawn will be kept and may be used in the study data analysis. Participants may withdraw at any time by informing the Research Coordinator and/or the PI. If a participant wants to withdraw or we choose to withdraw a participant, while she/he are using study equipment (i.e., one of the prostheses) we will arrange for the study prosthesis to be returned/removed and the participant's as-prescribed prosthesis to be re-fit.

6. Reporting

All safety information on AEs, SAEs, unanticipated events or problems, and protocol deviations will be collected. This information will be collected at study visits and whenever subjects call to report a problem. The information will be collected on VA IRB forms (Report of a SAE and/or Problem Form, or Report of Problems (ROP) Form) and in AE log forms as needed. Safety data will be collected on an as-needed basis and will begin upon enrollment into the study. All safety reporting requirements will be followed. Any anticipated AEs will be recorded on a log sheet and reported annually with the CRQ.

If we become aware of relevant findings or information that may affect subjects' health or welfare, we will contact subjects by phone and/or a letter to notify them.

Additional Safety Monitoring

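### Irritation, blisters and use periods ended early are reported or logged but never compared between systems, so Aim 2 judges skin health and comfort from end-of-period readings alone

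*Protocol*

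**What the plan says.** Protocol section 3 sets Aim 2: "Compare how three prosthetic systems effect residual limb skin health and comfort when participants pursue their usual activities". Three hypotheses serve it. Section 5.7 says of H2.1 that "The mean result from the three measures of skin hydration from the posterior compartment of the residual limb will be compared" and of H2.2 that "The mean result from the three measures of transepidermal water loss from the posterior compartment of the residual limb will be compared". H2.3 uses the Socket Comfort Score. Under section 5.5 all three are measured at the visit that follows two weeks on each system.

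Between visits, section 5.5 says "participants will be instructed to check their limb for redness and/or irritation twice a day" and tells them to contact staff about any issue. Section 5.6 names as possible harms "excessive skin dryness, blisters, or other soft tissue irritation while in the lab or during the at-home acclimation period". Section 6 says "Any anticipated AEs will be recorded on a log sheet and reported annually with the CRQ".

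The one planned event tabulation, in section 5.6, concerns injurious falls and component failures: "we will tabulate a list of any such reports that occur during the study and compare it with corresponding data available in the literature". For those who leave, section 5.8 says "All data previously collected from participants who withdraw or are withdrawn will be kept and may be used in the study data analysis". It arranges for the study prosthesis to be taken back and the as-prescribed one refitted, and asks for no measurement at that point.

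The SAP fits a linear mixed model with participant as random effect. It does not mention adverse events, periods ended early or missing periods.

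**The concern.** The trial is meant to show which system keeps the residual limb healthy and comfortable. The protocol's opening summary cites anecdotal reports of excessive dryness and discomfort with the perforated liner, so a problem specific to one system is foreseen.

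Blisters, redness and abandonment of a device are the most direct evidence on that question. The plan gathers some of this evidence for safety oversight but gives it no place in the comparison. Where a period ends early because of the skin or the fit, the end-of-period reading on that system may not exist. The participants a system suits least would then be the ones missing from its skin and comfort results.

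**Working it through.** **1. What is compared by system**

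| Evidence | Where collected | Planned comparison between systems |
|---|---|---|
| Hydration, water loss, Socket Comfort Score | 5.5, end-of-period visit | Yes (5.7, SAP) |
| Redness, irritation, blisters | 5.5 self-check and call; section 6 log | None |
| Period ended early for skin or comfort | 5.8, device returned | None |
| Falls, component failures | 5.6 | None; against the literature |
| Two-week step total | 5.7, Supplemental Measures | Yes, as a control for activity and wear |

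Neither study prosthesis has a skin or comfort reading before its own end-of-period visit. The as-prescribed prosthesis has a baseline reading, but the SAP does not assess differences from baseline. Someone who withdraws during the first period therefore has no end-of-period value on any system.

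**2. The plan's own figures**

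Inputs are from section 5.7, Statistical Power Analysis. The check is a paired t-test with two-sided alpha 0.05 (sidedness assumed) and noncentrality δ√n/σ, where σ is the standard deviation (SD) of the within-person difference.

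- Hydration: 9.3×√17/12.8 = 3.00, power 80.3% (stated 80%). 12.7×√20/14.4 = 3.94, power 96.2% (stated 96%).
- Water loss: 12.3×√20/13.0 = 4.23, power 98.0% (stated 97%). SD 18.8 gives 79.3% (stated 79%). SD 8.17 gives over 99.9% (stated 99%).

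The figures reproduce to within about one point. They assume a reading from every participant on each system. If 4 of 20 were lost at random, power would be 94.2% for water loss (SD 13.0) and 77.5% for hydration (9.3, SD 12.8; 86.9% with all 20). Random loss costs only precision; selective loss biases the estimate.

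**3. Selective loss (illustration; rates assumed)**

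Suppose the fraction f of participants with the largest within-person differences have no reading on the worse system. With q the standard normal quantile at 1−f and φ the normal density, the mean difference among complete pairs is δ − σ·φ(q)/(1−f). For water loss at f = 10%: q = 1.282, φ(q)/(1−f) = 0.195, and 12.3 − 13.0×0.195 = 9.77.

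| f | Water loss, complete pairs (true 12.3) | Water loss, random-intercept model | Hydration, complete pairs (true 9.3) |
|---|---|---|---|
| 5% | 10.89 | 11.5 | 7.91 |
| 10% | 9.77 | 10.8 | 6.80 |
| 15% | 8.73 | 10.1 | 5.79 |
| 20% | 7.75 | 9.5 | 4.82 |

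The model column comes from simulation: 20 participants, three systems, 600 runs per setting, averaged over assumed between-participant SDs of 4, 8 and 12. With no loss it returns about 12.25. Keeping a participant's other periods reduces the bias but does not remove it, because the missing value depends on a skin state nobody recorded.

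**4. A simpler illustration**

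Section 5.7 uses 16.5 and 28.8 g/m²/h for healthy and disrupted skin. If k of 20 stop a system with disrupted skin, its true mean is 16.5 + 12.3k/20: 17.73 for k = 2 and 18.96 for k = 4, against 16.5 among those measured. For comfort, if 3 of 20 would score 2 and 17 would score 7 (assumed), the true mean is (3×2 + 17×7)/20 = 6.25, against 7.0 recorded.

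**5. What a paired event comparison can show**

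With an exact McNemar test, six discordant pairs all in one direction give p = 2×0.5⁶ = 0.031; five give 0.0625. With about 20 participants the comparison is mainly descriptive.

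**The case against.** The best defence is that Aim 2 already measures skin harm. Section 3 presents hydration as a measure of dryness and water loss as a measure of barrier disruption, and irritated participants who attend are measured like everyone else. This stands. A reader might infer that none of the foreseen skin harms reaches Aim 2; the documents do not support that. What is left out is visible events. Three posterior readings per instrument on one day can miss a blister elsewhere or one that has healed.

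Other provisions also bear on the point. A period cut short would tend to lower the step total, which is compared across systems, but that total is an indirect wear check and does not measure tolerability. Section 5.5 allows another visit when data are missing, but this is optional, is not tied to early stops, and would come after the skin had changed. Adverse events are collected and the Medical Monitor reviews safety; that is oversight, not comparison by system.

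It is also fair that section 5.6 calls these harms possible and expects no problems at home, and that current skin irritation is an exclusion. The loss may prove small. The 28.8 comes from children with extrinsic atopic dermatitis, not prosthesis users. The shifts in step 4 (+1.23 and +2.46) are below one standard error of a paired difference, 13.0/√20 = 2.9. Step 3 is deliberately severe, since it removes exactly the worst differences.

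Finally, adding early readings to the two-week data would mix wear durations and change what is estimated. That is right, and the fix keeps them separate.

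**Conclusion.** The gap is real and limited. Visible skin events and early-ended periods have no planned comparison between systems, and no reading is required when a study prosthesis is stopped early. Followed as written, a system that caused blisters or was abandoned could look as good as the others, or better, on skin health and comfort.

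A reader might go further and infer that each system's worst cases do drop out, so that the Aim 2 results are biased. The documents do not show that: they give no early-stop rate, overall or by system. Under assumed selective loss of 5% to 20%, the mixed-model estimate of a 12.3 g/m²/h difference would be about 6% to 23% too small (11.5 to 9.5). With no early stops there would be no such bias, and only the missing tabulation would remain. The sample-size arithmetic is not in question. This is a cheap improvement worth making; H2.1 to H2.3 can still be tested as planned.

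**What to change.** In protocol section 5.7 and the SAP:

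1. Record each skin event and each early stop with the system worn. Report by system the number of participants with residual-limb irritation or blister, and the number ending a period early for skin or comfort reasons. Give paired differences with confidence intervals, label them mainly descriptive, and interpret H2.1 to H2.3 alongside them.
2. Where a participant who stops early is seen in the laboratory anyway, take the same hydration, water-loss and Socket Comfort Score readings. Keep them out of the primary two-week analysis. Use them in a sensitivity analysis that also treats early stops for skin or comfort reasons as unfavourable for that system.

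The cost is a few lines of text and some extra readings; no clinical or stopping rule changes. There are limits. Event capture is as-needed, so counts may be incomplete, and the documents do not say whether the log identifies the system worn. Early readings reflect shorter wear and may not be taken under the standard room, rest and skin-preparation conditions. The paired comparison has little power. The SAP is written in the past tense, so early-stop readings may no longer be obtainable; the tabulation should still be possible if event dates can be matched to use periods.
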